 5 • Determine and compare TG concentration before and after the intervention with fucoxanthin and
 6 placebo.
 7 • Determine and compare HDL-c concentration before and after the intervention with fucoxanthin and
 8 placebo.
 9 • Determine and compare fasting serum glucose level before and after the intervention with
 10 fucoxanthin and placebo.
 11 • Determine and compare insulin sensitivity before and after the intervention with fucoxanthin and
 12 placebo.
 13 • Determine and compare the total secretion of insulin before and after the intervention with
 14 fucoxanthin and placebo.
 15 • Determine and compare the first phase of insulin secretion before and after the intervention with
 16 fucoxanthin and placebo.

17 **Secondary objectives**

18 • Determine and compare body weight before and after the intervention with fucoxanthin and placebo.
 19 • Determine and compare BMI before and after the intervention with fucoxanthin and placebo.
 20 • Determine and compare body fat percentage before and after the intervention with fucoxanthin and
 21 placebo.
 22 • Determine and compare insulin concentration before and after the intervention with fucoxanthin and
 23 placebo.
 24 • Determine and compare post-load glucose concentration after oral administration of 75 g of glucose
 25 before and after the intervention with fucoxanthin and placebo.
 26 • Determine and compare total cholesterol (TC), LDL cholesterol (LDL-c), and VLDL before and after
 27 the intervention with fucoxanthin and placebo.
 28 • Determine and compare AST and ALT levels before and after the intervention with fucoxanthin and
 29 placebo.
 30 • Determine and compare creatinine and uric acid levels before and after the intervention with
 31 fucoxanthin and placebo.
 32 • Describe the tolerability of treatment with fucoxanthin and placebo.

34 **MATERIALS AND METHODS**

35 **Design**

36 Randomized, double-blind, and placebo controlled clinical trial.

37 **Universe**

38 Men and women aged 30 to 60 with a diagnosis of MeS, residing in the metropolitan area of Guadalajara.

39 **Sample**

40 The sample size was calculated using a formula for the difference in means in clinical trials. A confidence
 41 level of 95%, a power of 80%, the standard deviation, and the expected difference obtained from the response
 42 variables in patients with metabolic syndrome were considered.

$$43 n = 2 \left(\frac{(Z_\alpha - Z_{1-\beta})(\sigma)}{\delta} \right)^2$$

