44 • Z_α corresponds to the value of statistical confidence, which was pre-set at a 95% confidence level,
 45 for a type I error of 5% expressed as a two-tailed α value of 0.05. For this confidence level, the Z
 46 value was 1.96.

- 1 • $Z\beta$ represents the statistical power and was pre-set at the $Z_{1-\beta}$ value of 80% for a type II error of
2 20%, which corresponds to a β value of 0.20. For this statistical power, the standardized Z score was
3 0.842.
- 4 • σ is the standard deviation of waist circumference (WC), insulin sensitivity, and insulin secretion in
5 patients with MetS.
- 6 • δ is the expected difference in waist circumference, insulin sensitivity, and insulin secretion in
7 patients with MetS.

8 A total of 28 patients, 14 for each study group, was the result obtained with the highest number of required
9 patients, including an additional 20% to anticipate possible loss to follow-up.

10 **Criteria**

11 Inclusion criteria

- 12 • Age between 30 and 60 years
- 13 • Diagnosis of metabolic syndrome (MetS) according to the IDF criteria:
 - 14 ○ Waist circumference (WC) \geq 80 cm in women or \geq 90 cm in men, plus two or more of the
15 following elements:
 - 16 ▪ Systolic blood pressure (SBP) \geq 130 mmHg and/or diastolic blood pressure (DBP) \geq
17 85 mmHg
 - 18 ▪ Triglycerides (TG) \geq 150 mg/dL
 - 19 ▪ HDL cholesterol (C-HDL) $<$ 40 mg/dL in men or $<$ 50 mg/dL in women
 - 20 ▪ Fasting plasma glucose (FPG) \geq 100 mg/dL
 - 21 • BMI between 25.0 and 34.9 kg/m²
 - 22 • No pharmacological treatment for the components of MetS
 - 23 • Stable weight during the last three months (weight variation less than 10%)
 - 24 • Female participants declared the use of a contraceptive method to prevent pregnancy during the study
25 period
 - 26 • Signed written informed consent form

27 Exclusion criteria

- 28 • Women who are pregnant or breastfeeding
- 29 • History of kidney, thyroid, or liver disease
- 30 • Consumption of medications or supplements with proven properties that modify the behavior of
31 metabolic syndrome
- 32 • Glucose \geq 126 mg/dL or diagnosis of type 2 diabetes mellitus
- 33 • Total cholesterol (TC) $>$ 240 mg/dL
- 34 • Triglycerides (TG) $>$ 500 mg/dL

35 Elimination criteria

- 36 • Non-compliance of medication intake exceeding 20%
- 37 • Intolerance to any of the intervention ingredients
- 38 • Meeting an exclusion criterion during the study
- 39 • Experiencing a serious adverse event
- 40 • Withdrawal of consent

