43 **Outcome measures**

44 *Primary outcome measures*

- 45 • WC
- 46 • DBP
- 47 • SBP
- 48 • TG
- 49 • HDL-c
- 50 • Glucose
- 51 • Insulin sensitivity

- First-phase insulin secretion
- Total insulin secretion

Secondary outcome measures

- Body weight
- BMI (Body Mass Index)
- Body fat percentage
- Lipid profile (Total cholesterol, LDL-c, VLDL)
- Post-load glucose
- Insulin levels
- Liver enzymes (ALT, AST)
- Creatinine levels
- Adverse events

Measurement and evaluation procedures

Demographic determinations

- Age: Expressed in completed years at the start of the intervention.
- Sex: Referring to the phenotypic sex at birth, it was recorded as male or female.

Clinical determinations

- *WC*: It will be measured using a flexible measuring tape with the subject standing. The tape was placed parallel to the ground and without clothing at the measurement level. The tape was positioned at the midpoint between the costal margin and the iliac crests at the end of a normal exhalation.
- *Weight*: It will be measured with the participant standing in a bipedal position, wearing light clothing, without shoes, and with an empty bladder prior to measurement. A stationary bioelectrical impedance scale will be used.
- *BMI*: It will be obtained by calculating the ratio of body weight in kg to the square of height in meters.
- *Body Fat*: It was determined using scale that utilizes the bioelectrical impedance method. Through a low-frequency signal, it calculates body fat and body composition.
- *SBP/DBP* (Systolic Blood Pressure/Diastolic Blood Pressure): It was determined using a digital sphygmomanometer. The participant was in a seated position after at least 5 minutes of rest. The cuff will be placed 3 cm above the elbow fold of the left arm. Two measurements will be taken to obtain the average blood pressure.

Clinical laboratory procedures

Oral Glucose Tolerance Test (OGTT)

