- *Insulin*: For the determination of insulin, the enzyme-linked immunosorbent assay (ELISA) sandwich method was used. In this technique, samples and the conjugate reagent (biotinylated anti-insulin and HRP) are added to a streptavidin-coated surface. Insulin in the serum binds to the corresponding antigen pair, forming a sandwich complex, which immobilizes on the surface. After the addition of a substrate, a chromatic reaction occurs proportional to the insulin concentration. CVa = 3.1%, CVe = 4.5%.

40 Calculations

41 C-LDL and VLDL concentrations:²²

42 Formula de Friedewald: $C-LDL = CT - \left(C-HDL + \frac{TG}{5} \right)$ $VLDL = \frac{TG}{5}$

43 Glucose and insulin AUC: The calculation was performed using the mathematical formula proposed by
44 Tai..²³

45
$$\text{Area} = \frac{1}{2} \sum_{i=1}^n x_{i-1} (y_{i-1} + y_i)$$

46 Indices

47 Matsuda Index: It is used to calculate insulin sensitivity using the following formula:²⁴

48 Matsuda index =
$$\frac{10000}{\sqrt{(Gluc_0 * Ins_0) * (Gluc_{\text{mean } 0-120} * Ins_{\text{mean } 0-120})}}$$

Stumvoll Index: It is used to calculate the first-phase insulin secretion using the following formula.²⁵

$$\text{Stumvoll index} = 1,283 + 1.829 \times \text{Ins}_{30} - 138.7 \times \text{Gluc}_0 + 3.772 \times \text{Ins}_0$$

Total insulin secretion: It is used to calculate the first-phase insulin secretion using the following formula.²⁶

$$\text{Total insulin secretion} = \frac{\text{AUC Insulin}_{0-120}}{\text{AUC Glucose}_{0-120}}$$

Other determinations

Adherencia al tratamiento

Each participant will be given an adherence and monitoring diary in which they will be asked to record each intake of the intervention capsules. This diary is designed to record the date and time of each intake for a period of 12 weeks.

During each visit throughout the intervention, the patient will be asked to return the assigned intervention bottle containing any capsules that have not been taken, in order to calculate and estimate the adherence percentage.

Adverse events

The patient will record in the adherence and monitoring diary any symptoms or adverse changes in their health status during the medication intake period. A direct contact telephone number with the investigators will be provided to consult and report any unforeseen events.

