During each visit throughout the intervention, the patient will be interviewed and physically examined, if necessary, in search of changes in health status that may be related to the consumption of the formulation's ingredients.

Grupos de estudio y administración de la intervención

Two groups of 14 patients each will be formed:

- Fucoxanthin: Each patient will receive a capsule containing 12 mg of fucoxanthin every 24 hours. They will ask to take one capsule with the first bite of breakfast for a duration of 12 weeks.
- Placebo: Each patient will receive a placebo capsule (Magnesium stearate) that is indistinguishable from fucoxanthin. They will be instructed to take one capsule with the first bite of breakfast for a duration of 12 weeks.

Allocation of intervention and blinding

The treatment assignment will be performed through simple randomization, using the method of a simple random number table. By using computer software, each intervention will be randomly assigned an identification with a numerical code corresponding to an identified intervention within Group A or Group B. The patient and the researcher will not be informed of which pharmacological intervention corresponds to each numerical code.

DATA COLLECTION AND STATISTICAL ANÁLISIS PLAN

All the results will be collected in a digital database designed for this study, where no confidential personal information not related to the study variables will be recorded. The information entered in the database will be transferred for analysis in the statistical software IBM SPSS Statistics® for Windows®. The statistical analysis will be conducted at the end of the total data collection once the intervention in the included patients has finished. All patients will be included in the intention-to-treat analysis. In descriptive statistics, measures of central tendency and dispersion will be used. Quantitative variables will be presented with means and standard deviations. Qualitative variables will be presented with frequencies and percentages.

The Shapiro-Wilk test will be performed to determine the normality of the sample distribution in each variable. If the sample distribution is found to be abnormal, non-parametric tests will be used. The analysis between groups (independent samples) will be analyzed using the Mann-Whitney U test for quantitative variables, and the X² test or Fisher's exact test for qualitative variables. Intragroup analysis (two related

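### AST, ALT and creatinine get only group summaries and group tests, so nothing planned shows how many patients had a large rise or brings a symptomless one into the tolerability description

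*Combined protocol and SAP*

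**What the plan says.** Under Secondary objectives, AST and ALT have their own entry, "Determine and compare AST and ALT levels before and after the intervention with fucoxanthin and" placebo. Creatinine is paired with uric acid in a similar entry. Tolerability is a further, separate entry, to be described. Liver enzymes, creatinine and adverse events then appear as separate items among the secondary outcome measures.

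The section on data collection and statistical analysis has one rule for all such variables: "Quantitative variables will be presented with means and standard deviations". If Shapiro-Wilk indicates non-normality, Mann-Whitney is used between groups and Wilcoxon within groups. No parametric test is named. Chi-square or Fisher's test is reserved for qualitative variables, and no laboratory value is made into one. The section has no upper limit of normal, shift count, largest rise or patient listing.

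For adverse events, the diary is to record "any symptoms or adverse changes in their health status". A telephone contact and an interview at each visit, with physical examination when needed, complete the capture. The elimination criteria refer back to the exclusion criteria, which name a history of kidney or liver disease but no enzyme or creatinine limit.

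**The concern.** Liver or kidney harm from a supplement, if it occurs, is likely to appear as a marked rise in one or two people and not as a shift of the whole arm. A rank test uses only the order of the values, so it cannot tell a small rise from a very large one. A t test loses power because the extreme value inflates the SD it is judged against. If the patient has no symptoms, the diary and interview need not pick up the rise either.

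The Rationale says that safety in this population still has to be established. If the plan is followed to the letter, a reader would get group summaries and p-values for these tests and a tolerability description drawn from symptoms. Nothing written would connect the two.

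**Working it through.** **Step 1. The plan's own figure.** The documents give 14 per arm (28 in all) after a 20% allowance for loss, "for a type I error of 5% expressed as a two-tailed α value of 0.05", and 80% power (Z values 1.96 and 0.842). The figure cannot be reproduced because σ and δ have no values. A base of 11 per arm is compatible: 11/0.8 = 13.75 or 11 × 1.2 = 13.2, each rounded up to 14. With the Z values summed, 11 per arm implies δ/σ = (1.96 + 0.842) × √(2/11) = 1.19. (The formula is printed with a minus sign, which does not affect this point.) What matters is that "σ is the standard deviation of waist circumference (WC), insulin sensitivity, and insulin secretion in" patients with MetS, so no laboratory safety variable entered the calculation. Only n = 14, or about 11 after losses, is carried forward.

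**Step 2. How far one patient can move the rank test.** The Mann-Whitney statistic U counts active-placebo pairs in which the active value is higher. With 14 per arm and no effect, its SD is √(14 × 14 × 29/12) = 21.8. An average active patient contributes 7 to U. A patient above every placebo value contributes 14, whatever the size of the rise. One such patient therefore shifts U by about 7/21.8 = 0.32 SD, and two by about 14/21.8 = 0.64 SD, against the 1.96 needed. In a fixed example with two top values, the exact p-value is 0.376 whether they stand at 20, 120, 200 or 1000.

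**Step 3. Simulation A.** Assumptions not in the documents: ALT lognormal, mean 28, CV 45%; k fucoxanthin patients multiplied by 10; end values compared; 14 per arm. Ranges are over repeat runs, and the spread is simulation error.

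| k | Mann-Whitney p ≤ 0.05 | t test p ≤ 0.05 |
|---|---|---|
| 0 | 4.6% to 4.8% | 4.7% to 5.1% |
| 1 | 4.2% to 5.5% | 0.2% to 0.4% |
| 2 | 6.7% to 7.2% | 0.5% |
| 3 | 11.8% to 12.4% | 5.6% |

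**Step 4. Simulation B, using change from baseline.** Assumptions not in the documents: lognormal ALT, mean 25, SD 10, within-patient correlation 0.7, upper limit 40; 14 per arm; 2,000 trials per row.

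| Fucoxanthin patients with a rise | Mann-Whitney on change | Wilcoxon within arm |
|---|---|---|
| none | 5.3% | 5.9% |
| one at 3 × limit | 4.8% | 5.4% |
| one at 5 × limit | 5.1% | 4.9% |
| two at 3 × limit | 8.4% | 9.5% |
| two at 5 × limit | 6.3% | 9.0% |

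With 11 per arm and one or two such patients, Mann-Whitney on change lies between 4.7% and 7.4%.

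**Step 5. What the planned mean and SD would show.** Under simulation B, one patient at 3 × 40 = 120 moves the arm mean from 25 to (13 × 25 + 120)/14 = 31.8, and the SD from about 10 to 27. At 5 × 40 = 200 the mean becomes (13 × 25 + 200)/14 = 37.5 and the SD about 48. Under simulation A, one tenfold rise moves a typical arm from about 28 (SD 12) to 44 (SD 62). The SD then exceeds the mean in about 85% of trials, against 0.04% with no such patient.

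**Step 6. Would testing a count help?** Fisher's test gives p = 1.00 for 1/14 against 0/14, 0.48 for 2/14, 0.098 for 4/14 and 0.041 for 5/14. Even 0/14 leaves an exact two-sided 95% upper limit of 1 − 0.025^(1/14) = 23.2%. Any addition should therefore be descriptive.

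**Step 7. Chance crossings of a limit.** With simulation A's distribution, an assumed limit of 40 and correlation 0.7, about 7% of untreated patients move from within to above the limit. That is 14 × 0.07 ≈ 1 per arm, and at least one in about 65% of arms (1 − 0.93^14 = 64% from the rounded 7%).

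**The case against.** The strongest reply is that the planned table would usually give the problem away. A reader might infer from the test results that a large rise would be invisible. The documents do not support that, because the plan requires means and SDs, and in step 5 an arm with one tenfold rise usually has an SD larger than its mean. This stands. The table still does not say how many patients were affected, how high they went or whether they started within the limit, and smaller rises are harder to see.

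A reader might also infer that tolerability will be judged by a laboratory p-value. The documents never say so: tolerability is a separate objective, to be described, with no test assigned. That stands too. The gap is the absence of any link between the laboratory results and that description, not a wrong link.

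Nor does the plan commit to rank tests alone, since they depend on Shapiro-Wilk. In practice one tenfold rise makes Shapiro-Wilk reject normality in the affected arm in 99.8% to 99.9% of simulated trials, so the rank test is the likely route. The t-test figures describe a branch that would rarely be taken.

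Finally, the plan is short and specifies no listings for any outcome, and a listing could be produced at reporting without prior mention. That is true, and it makes this an inexpensive improvement in reporting. It does not reveal a bias in any estimate.

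**Conclusion.** The point holds in a limited form. AST, ALT and creatinine are covered only by the general rule for quantitative variables. With 14 per arm, the planned tests respond to one or two large individual rises at little more than their false-positive rate: about 4% to 6% for one patient and 6% to 10% for two, across both sets of assumptions and both rank tests. These rates rest on assumed lognormal ALT distributions, since the documents give none, but step 2 shows that the weakness of the between-group rank test follows from the sample size alone.

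It would go too far to conclude that the analysis cannot show harm at all, because the mean and SD may signal an extreme rise. What is missing is the number of patients affected, the size of their rises, and any written route from a symptomless laboratory rise to the adverse-event or tolerability description.

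**What to change.** In the section on data collection and statistical analysis, add that AST, ALT and creatinine are also reported descriptively by arm, without a further test:

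- a listing of baseline and end-of-treatment values for every patient with a value above the laboratory's upper limit;
- the largest individual rise relative to baseline in each arm;
- as context only, the number per arm moving from within to above the limit, read against placebo because some crossings occur by chance.

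State that the tolerability description takes these into account alongside the events from the diary and interviews. Any clinical threshold is for the investigators to set.

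The cost is one extra table and one listing from measurements already planned, with no new visits or samples.

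### The printed sample-size formula subtracts a power term given as +0.842, so as written it does not deliver 80% power, and the plan lacks the inputs to show which sign produced 14 per arm

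*Combined protocol and SAP*

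**What the plan says.** Under Materials and Methods, Sample, the plan uses a difference-in-means formula. Inside the squared bracket it contains "Z_\alpha - Z_{1-\beta})(\sigma", so the power term is subtracted from the alpha term.

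The bullets below define the terms:

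- Z for alpha is 1.96, for a two-tailed alpha of 0.05.
- The power bullet is headed Z-beta, but says that it "represents the statistical power and was pre-set at the" Z(1-beta) value of 80%. It adds: "For this statistical power, the standardized Z score was" 0.842. No minus sign is attached.
- Sigma "is the standard deviation of waist circumference (WC), insulin sensitivity, and insulin secretion in" patients with MetS. No number follows.
- Delta "is the expected difference in waist circumference, insulin sensitivity, and insulin secretion in" patients with MetS. No number follows.

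The result is then stated: "A total of 28 patients, 14 for each study group, was the result obtained with the highest number of required" patients, "including an additional 20% to anticipate possible loss to follow-up". The outcome that gave this largest requirement is not identified. No source is given for sigma or delta, and no redaction mark appears in the section.

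**The concern.** In a two-sample formula of this kind the alpha and power terms add when both are written as positive upper-tail scores. Subtracting them makes the required n fall as the desired power rises, which cannot be right for any sigma and delta.

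The 80% is the plan's only statement of what the trial can detect. If the calculation used a plus, the error is confined to the printed formula and the sample size stands. If it used the minus, the trial was sized for about 20% power at its own assumed effect, and a null result would say little. The two cases differ greatly in consequence, and a reader of the plan cannot tell which applies.

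**Working it through.** **Inputs from the Sample subsection:** Z for alpha 1.96; Z for power 0.842; 14 per arm including 20% for loss. Sigma and delta are not given, so 28 cannot be reproduced forwards with either sign. What can be done is to test the formula and then invert it.

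**1. The formula as printed against the additive form**

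- Printed: 1.96 - 0.842 = 1.118; n per arm = 2 x 1.118^2 x (sigma/delta)^2 = 2.50 (sigma/delta)^2.
- Additive: 1.96 + 0.842 = 2.802; n per arm = 2 x 2.802^2 x (sigma/delta)^2 = 15.70 (sigma/delta)^2.
- Ratio: (2.802/1.118)^2 = 6.28.
- Power if the printed form is used: Phi(1.118 - 1.96) = Phi(-0.842) = 0.20.

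**2. A check that needs no sigma or delta.** Ask for 90% power (Z = 1.282) in place of 80%.

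- Printed: (1.96 - 1.282)^2 / 1.118^2 = 0.460/1.250 = 0.368, so n falls by 63%.
- Additive: (1.96 + 1.282)^2 / 2.802^2 = 1.339, so n rises by 34%.

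**3. The number before the loss allowance.** The plan does not say how the 20% was added. 11 x 1.2 = 13.2 and 11/0.8 = 13.75 both round up to 14; 12 x 1.2 = 14.4 rounds to 14. Any unrounded result just above 10 rounds up to 11, so the formula's output before rounding lies at about 10 to 12 per arm.

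**4. The standardised effect implied by 14 per arm:** d = multiplier x sqrt(2/n).

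| Unrounded n before loss | d with plus | d with minus |
|---|---|---|
| 10 | 1.25 | 0.50 |
| 11 | 1.19 | 0.48 |
| 12 | 1.14 | 0.46 |

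Both columns lead to 14 per arm, so the stated total does not identify the sign.

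**5. Power at those effects** (two-sided t-test at 0.05, noncentral t). This is an approximation: the analysis section names Mann-Whitney for non-normal data and does not name the between-group test for normal data.

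- Minus-form effects: 0.175 (d = 0.456, 11 per arm) to 0.247 (d = 0.50, 14 per arm), that is about 18% to 25%.
- Plus-form effects with all 14 per arm: 0.830 (d = 1.144) to 0.889 (d = 1.25). With 11 per arm: 0.760 at d = 1.195 and 0.796 at d = 1.25. With 12 per arm: 0.764 at d = 1.144.
- Effect needed for 80% power, whichever sign was used: about 1.10 SD with 14 per arm, 1.20 SD with 12, 1.26 SD with 11.

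**6. Size needed for 80% at the minus-form effects:** 6.28 x 10 = 62.8, so 63 per arm; 6.28 x 12 = 75.4, so 76 per arm, both before loss.

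**The case against.** The best answer is that the minus is notation. Writing Z-alpha minus Z-beta is valid when Z-beta is the lower-tail quantile, which is negative (-0.842 at 80% power). The power bullet is headed Z-beta, so the authors may have mixed that convention with the Z(1-beta) symbol and its positive value. The formula was also read from a PDF by a program, so the sign itself carries some uncertainty. This is a sufficient explanation and may well be the true one. It does not rescue the text as it stands: the formula uses Z(1-beta), the value given is positive, and no other part of the plan reconciles them.

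A reader might infer that the trial has only 20% power, or that 28 is a wrong number. The documents do not support that. Without sigma and delta no calculation contradicts 28, and under the plus form it follows from an effect of about 1.14 to 1.25 SD.

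A reader might also try to settle the sign from the waist changes quoted in the Background. That is not a valid test. The plan does not say that it used those figures, waist need not be the outcome that drove the maximum, the change quoted for the seaweed trial in MetS patients is reported for the intervention group and not as a difference from placebo, and the cited trials give very different answers.

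Unstated sigma and delta would, alone, be missing detail. They carry weight here because they are the only means of telling which sign was used.

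**Conclusion.** The point holds as an error in the printed rule together with a calculation that cannot be verified. Taken literally, the formula and its stated Z values give an n 6.28 times too small for the claimed 80% power. Whether that error entered the actual calculation is unknown. This should be corrected, but it is not a demonstrated failure of the sample size.

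The conclusion assumes that the minus sign in the PDF text is what the plan prints, and that about 10 to 12 per arm came before the 20% allowance. The multipliers, the 6.28 ratio and the 63% against 34% check depend on neither sigma nor delta. The power figures of 18% to 25% apply only if the minus was used, and rest on the t-test approximation. Separately from the sign, the plan does not tell its reader that 14 per arm reaches 80% power only for an effect of about 1.1 SD, or about 1.2 to 1.26 SD if 12 or 11 per arm remain.

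**What to change.** Write the formula as n = 2[(Z-alpha + Z(1-beta)) x sigma/delta]^2 and use one symbol for the power term in the formula and its bullet. Rerun it with the sigma and delta actually used. Print those values with their source, name the outcome that gave 14 per arm, and say how the 20% was applied.

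If the plus form reproduces the number before loss, keep the 80%. If the minus was used, replace the 80% with the power that 14 per arm, and the number left after the planned loss, give at that delta. Keeping 80% at that delta would instead take about 63 to 76 per arm before loss; that figure shows the size of the gap and is not the change recommended here.

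The cost is one recalculation and a rewritten paragraph. The stated power may become less favourable, but no added patients are required by this fix.

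### The criteria require untreated patients and cap glucose, cholesterol and triglycerides, but give no blood pressure level for refusing entry

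*Combined protocol and SAP*

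**What the plan says.** All of this is in the combined protocol and SAP, under Materials and Methods.

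- **Inclusion criteria.** Metabolic syndrome is defined by waist circumference "plus two or more of the" listed elements. One of the four is raised blood pressure, given as a floor: SBP at or above "130 mmHg and/or diastolic blood pressure (DBP") at or above 85 mmHg. A separate line requires "No pharmacological treatment for the components of MetS".
- **Exclusion criteria.** Glucose at or above "126 mg/dL or diagnosis of type 2 diabetes mellitus", total cholesterol above 240 mg/dL, triglycerides above 500 mg/dL, prior kidney, thyroid or liver disease, and "Consumption of medications or supplements with proven properties that modify the behavior of" the syndrome. Blood pressure, hypertension and cardiovascular disease are not mentioned.
- **Elimination criteria.** These include a serious adverse event and "Meeting an exclusion criterion during the study".
- **Outcome measures.** SBP and DBP are both listed under "Primary outcome measures".
- **Clinical determinations.** For blood pressure, "Two measurements will be taken to obtain the average blood pressure". No level triggers any action.
- **Study groups.** Both arms take one capsule daily for 12 weeks.

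**The concern.** The entry rule selects people who take no drug for any component of the syndrome, and blood pressure is one of those components. A candidate with very high untreated pressure is the one who most clearly needs an antihypertensive, and the written rule has no line at which that candidate is turned away and referred.

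Neither arm is an established blood pressure treatment. One is placebo, and the Rationale section itself describes fucoxanthin's effect on blood pressure as inconsistent. What is at stake is the safety of a patient who is enrolled when referral was the better course. Severe hypertension can be present without symptoms, so safeguards that wait for a complaint or an event may not detect it.

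**Working it through.** The plan has no figure of its own to reproduce here. The check compares each criterion with the question of whether it sets an upper limit.

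| Variable | Role at entry | Upper limit for entry |
|---|---|---|
| Waist circumference | Required: 80 cm or more (women), 90 cm or more (men) | None |
| SBP / DBP | Optional element: SBP 130 or more and/or DBP 85 mmHg or more | **None** |
| Triglycerides | Optional element: 150 mg/dL or more | Excluded above 500 mg/dL |
| HDL-c | Optional element: below 40 (men), below 50 mg/dL (women) | None; the element is a low value |
| Fasting glucose | Optional element: 100 mg/dL or more | Excluded at 126 mg/dL or more, or with type 2 diabetes |
| Total cholesterol | Not an element | Excluded above 240 mg/dL |
| BMI | Required: 25.0 to 34.9 kg/m² | 34.9 kg/m² |

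**Step 1. Apply the criteria to an illustrative patient.** Take an untreated person at 185/115 mmHg (an illustrative value, not from the documents). Age is 30 to 60, BMI is within range, and waist circumference qualifies. Triglycerides lie between 150 and 500 mg/dL, glucose is below 126 mg/dL and total cholesterol is at most 240 mg/dL. There is no kidney, thyroid or liver disease, and the remaining lines (stable weight, contraception, consent) are met. Waist plus two elements (blood pressure and triglycerides) satisfies the definition, and no exclusion applies. The patient is eligible for either arm, for 12 × 7 = 84 days.

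**Step 2. Check whether a later rule covers the case.**

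- The diary and telephone line (Adverse events section) depend on the patient noticing something.
- The visit interview includes an examination only where thought necessary, and no blood pressure level is attached.
- Elimination for a serious adverse event follows the event.
- The rule "Meeting an exclusion criterion during the study" has no blood pressure trigger, because no exclusion criterion concerns blood pressure.
- Ethics approval and oversight (Ethical considerations section) set no level.

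**Step 3. Ask how often this could happen.** The documents give no distribution for the target population. The only SBP figure for patients with metabolic syndrome is 128.1 ± 8.4 mmHg, from a cited trial with n = 14 (Clinical trials section). If ± is a standard deviation, which is not stated, then (160 − 128.1) / 8.4 = 31.9 / 8.4 = 3.8 standard deviations above the mean. That suggests such patients may be rare. The evidence is thin: the sample is small, and the protocol does not say whether those patients were untreated. No probability is claimed.

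**The case against.** The strongest reply is that eligibility permits enrolment and does not compel it. A reader might infer that the protocol commits a severely hypertensive patient to 12 weeks without treatment. The documents do not support that: nobody is obliged to enrol such a patient or keep them in, and nothing forbids treatment. The study was classed as greater than minimal risk, was approved by an ethics committee and declares adherence to the Helsinki principles. The kidney-disease exclusion may also remove some patients at higher risk. All of this stands, and it narrows the point to the absence of a written level for refusing entry.

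A second tempting inference is that three laboratory caps and none on blood pressure prove an oversight. They do not. The plan gives no reason for the caps, and the glucose cap, paired with diabetes, may simply define the population. Waist circumference and HDL-c have no exclusion limit either. The safety argument has to stand without the asymmetry, and it does.

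A third inference would be that the gap biases the results because SBP and DBP are primary outcomes. Nothing in the documents shows that.

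Finally, frequency is unknown and the documents do not define severe hypertension, so any threshold comes from outside them. Both are correct and limit the weight of the point. Among 28 planned patients there may be no such case. The written rule would still admit one.

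**Conclusion.** The gap is real and confined to eligibility: the criteria and the rest of the protocol contain no upper blood pressure level, and an untreated patient with severe hypertension can satisfy every written condition for randomisation. The existing protections are genuine but reactive or unspecific.

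Its size cannot be put as a probability. It rests on the consequence for an individual patient. The assumptions are the meaning given to severe (160/100 to 180/110 mmHg) and that such a candidate might present at all. The point is a cheap safety improvement, held with medium confidence. The removed consent pages could not be checked and are not counted as missing.

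**What to change.** Add one exclusion criterion, worded for screening only: *at screening, mean of the two readings SBP ≥ 160 mmHg or DBP ≥ 100 mmHg; refer for treatment.* The value is an assumption, with a reasonable range up to 180/110 mmHg, and the investigators and ethics committee should confirm it.

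The words *at screening* are essential. Without them, "Meeting an exclusion criterion during the study" would remove randomised patients because of their value on a primary outcome.

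**Cost.** One line of text and no new procedure, provided the two-reading average already described is used at screening. A few candidates would be lost; the documents do not allow the number to be estimated.

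**What not to add on its own.** An in-study referral level would conflict with the present rules. An antihypertensive started after referral would plausibly meet the exclusion for drugs that modify the syndrome, and so trigger elimination. It should be added only if the elimination rule is also amended to exempt antihypertensives started for safety. The screening line needs no such change.
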